1 INTRODUCTION/BACKGROUND

This statistical analysis plan (SAP) describes the data analysis specifications for MicroTransponder, Inc. Protocol MT-St-03 (Stroke) entitled “A Pivotal Randomized Study Assessing Vagus Nerve Stimulation (VNS) During Rehabilitation for Improved Upper Limb Motor Function After Stroke (VNS-REHAB).” This version of the SAP is based on protocol Version 1.1, 23 March 2017.

This SAP follows the International Conference on Harmonisation (ICH) Guidelines E3 and E9. All statistical analyses will be performed using SAS[®], Version 9.4 or higher. Differences in the analyses from those described in the study protocol will be described in Section 5.2 of this document.

This is a pivotal study designed to provide information on the clinical use of vagus nerve stimulation (VNS) during upper limb motor rehabilitation (standard of care) for the treatment of upper limb deficits associated with stroke. The study is proposed as primary support for US market approval; it is expected to give safety and efficacy information.

This Statistical Analysis Plan addresses data collected in Phase I of this study, and is intended to provide safety and efficacy results to support filing for market approval. Data from Phases II and III will then be analyzed separately at a later date.

2 STUDY OBJECTIVES

The goal of this study is to show that VNS performed during rehabilitation for subjects with upper limb motor deficits following stroke will provide more benefit than active-control (rehabilitation only) after 6 weeks of therapy. Additionally, VNS Therapy for stroke rehabilitation will be as safe as it is for epilepsy and depression.

2.1 Primary Objective

The primary objectives of this study are to assess:

- the efficacy of VNS therapy compared to standard rehabilitation (active control includes the surgical intervention and sham stimulation) in the recovery of upper limb motor function after stroke.
- safety of the surgical intervention and VNS stimulation

2.2 Secondary Objectives

The secondary objective is to provide evidence that VNS coupled with rehabilitation provides quality of life improvements, such as improved function in daily activities.

3 STUDY DESIGN

This protocol is a pivotal study of up to 120 subjects and 15 clinical sites. All subjects are implanted with the Vivistim System[®] and then randomized to either study treatment or active-control treatment. Study treatment is vagus nerve stimulation (VNS) delivered during rehabilitation. Active control treatment is rehabilitation (standard-of-care treatment) with only a minimal amount of VNS at the start of each session intended to support blinding.

This study has three distinct stages:

Stage I – blinded, with consent, assessment, implant, baseline assessment, acute therapy (6 weeks), and follow-up assessment periods (Days 1, 30 and 90 post-acute therapy)

Stage II – unblinded follow-up, including additional therapy sessions and quarterly assessments through one year post implant. Control group subjects crossover to VNS treatment.

Stage III - annual (yearly) follow-up through commercial approval to allow the device to remain implanted and the subject to continue at-home use. Additional rehabilitation sessions are allowed at the investigator's discretion.

This statistical analysis plan (SAP) is focused on Stage I (blinded, randomized portion). A future SAP will focus on Stage II and Stage III, and will be developed prior to the first subject completing Stage II (first subject reaching one-year post implant).

3.1 Randomization

Subjects will be randomized 1:1 on the day of implant surgery to either the device treatment (rehabilitation and VNS) or control (rehabilitation and Control VNS) groups. An approved, unblinded person at each site accesses the subject's group assignment via an electronic (web-based) system.

Randomization will be stratified by FMA-UE score (20 to ≤ 35 ; >35 to 50), and age (≤ 30 , >30), within each region (North America vs ROW). Therefore, there are eight (8) randomization assignment tables. When a study site (linked to a region) submits the Randomization form with the subject's FMA-UE score, age, the Clinical Discovery Platform (CDP) will assign the next available treatment assignment from the corresponding randomization table.

3.2 Delivery of VNS Therapy and Treatment Blinding

Subjects in both groups are treated similarly. At each visit, subjects in both groups will receive stimulation via a push-button press for their first 4 rehabilitation movements (4 stimulations), starting at 0.8 mA and reducing in 0.2 mA steps (depending on perception), such that subjects barely perceive or do not perceive the fourth stimulation. This is done to help facilitate blinding.

Thereafter, therapists will continue to use a push-button to initiate stimulation for both groups throughout the therapy sessions; however, only the VNS group receives stimulation. All subjects will be told that they may or may not feel the stimulation during therapy - only about one half of the UK pilot study subjects felt stimulation at 0.8 mA and only about 25% of the subjects in the US IDE study felt 0.8 mA stimulation. Furthermore, subjects in both groups will be told that

they may initially feel the stimulation, but that it is possible that they may acclimate to the stimulation (as also occurred in the UK study and occurs in epilepsy). These efforts, along with the fact that all subjects will receive the same type of rehabilitation and be treated similarly, will help to maintain the blind.

Assessments are performed by a blinded assessor who does not perform therapy on the same subject. A blinded assessor may perform therapy on some subjects and perform assessments on other subjects, but should not perform assessments and therapy on the same subject. Whenever possible, the same assessor should perform the V4, V5, V6 and V7 assessments for a single subject. Sponsor approval is necessary if a different assessor will be used for the same subject at V4 and V5. This separates treatment from assessment and reduces the possibility of an assessor guessing information on group assignment (based on adverse event or subject comment).

3.3 Study Schedule and Treatment

Stage I: Subjects will be screened and assessed for upper limb paresis associated with stroke using a detailed stroke history evaluation (including type, location, onset, neurological evaluation, etc.) and various assessment scores to determine the level of disability in performing everyday tasks. Clinical evaluations by a stroke expert will confirm subjects entering the study exhibit a moderate to severe motor impairment in the upper extremity (UE) (as indicated by a FMA-UE score of 20 to 50) and have at least a nine-month history of the disorder. After informed consent signature, repeat assessments and other measurements will be recorded prior to randomization. Subjects will maintain their group assignments through Visit 7 (end of Stage I, assessment follow-up).

Subjects will start study therapy after an approximately one-week recovery period after surgery. This time period may vary depending on schedules and subject recovery times. The assessments after surgery, and before treatment (Visit 4) will be the baseline for statistical analyses. After a 6 week acute treatment period, post treatment assessments will be done at Visit 5 (1 Day post treatment), Visit 6 (30 Days post treatment), and Visit 7 (90 Days post treatment). During this 90 day post treatment period, subjects will not receive in-clinic rehabilitation, but are given a magnet to swipe just prior to performing their in-home rehabilitation for 30 minutes daily. The magnet activates VNS in the VNS group subjects but does not activate VNS in the Control subjects.

Stage II: Stage II begins after Visit 7 (Day 90 post treatment). It will be the Investigator's and subject's decision to continue treatment during this unblinded follow-up stage. The intent is that all subjects will be followed through at least 12 months of post-acute study. All original VNS group subjects continue at-home rehabilitation and home-initiated stimulation for 30 minutes daily and all original Control group subjects start a 6-week rehabilitation session plus active VNS. The assessments at Visit 7 will serve as Baseline for Stage II. The control subjects will have 6 weeks of rehabilitation sessions plus active VNS treatment, followed by assessment Visits LT1 (Day 1 after the 6 week treatment), LT2 (Day 30 post treatment) and LT3 (Day 60 post treatment; at Month 3 of Stage II). All subjects will then have Visits LT4 (Month 6 of Stage II) LT5 (Month 9) and LT6 (Month 12). Different stimulation settings may be tried during the long-term therapy, especially in non-responders (those with less than a 6-point FMA-UE change).

Study guidelines allow subjects to continue at-home stimulation for 30 minutes a day while performing rehabilitation movements at home, as designated by the therapist.

All continuing subjects will have two more in-clinic rehabilitation sessions with VNS for one week (“booster sessions”), approximately one month prior to LT4 (Month 6), and LT6 (Month 12) assessments. Subjects will also be able to utilize daily subject-initiated stimulation during in-home rehabilitation.

Stage III: After Stage II of VNS therapy, subjects who wish to continue VNS use must have at least annual follow-up visits. Those who do not have annual visits or who wish to discontinue will have their device systems explanted.

3.4 Sample Size Calculation/Justification

The study plan is to enroll and implant up to 120 subjects in order to have approximately 100 subjects complete the study. A sample size of 100 subjects total (50 per group) will have 80% power with 0.05 alpha to detect a difference of 2.3 with SD=4.0 on the FMA UE scale between the two treatment groups. This is based on the assumption of VNS having an average improvement of 7.5 from baseline, with control having an average change of 5.2 from baseline. A sample size of 50 per group will have over 95% power at 0.05 alpha to show a difference in responders (defined as an improvement of 6 points or more from baseline), assuming 75% response in the VNS group and 33% in the control group. With respect to safety, a sample of at least 100 subjects implanted and receiving VNS allows adequate power to detect the incidence of safety and device events. A sample of 100 subjects yields 95% probability that the study will reveal at least one occurrence of all events or complications that occur in subjects at a rate of 3% or greater. In addition, implantation and follow-up of 100 subjects for 6 weeks will yield 4200 subject-days (600 weeks or over 11 years) of total exposure.

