4 ANALYSIS SETS & SCHEDULE

4.1 Intent to Treat (ITT)

The ITT population will include any subject who is randomized, and will be the basis of the efficacy and safety analyses. All subjects who undergo surgery will be included in the safety population, with all adverse event and safety information reported.

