5.4 Study Hypothesis Testing

The primary objectives are to assess the efficacy and safety of 6 weeks of VNS therapy performed during rehabilitation for subjects with upper limb motor deficits following stroke. .

The primary efficacy analysis will be based on the change of the FMA UE score from baseline (Visit 4) to Visit 5 (Day 1 post therapy). The null hypothesis is the change in FMA UE is not different between VNS treatment and control sham treatment, with significance at alpha 0.05 two sided.

Three secondary endpoints will each be tested for significance with 0.05 Type I error (two sided) in a hierarchical manner. Significance will be declared for the first secondary endpoint at 0.05 only if the primary is significant at 0.05, and each subsequent endpoint only if all higher ranked endpoints were significant at 0.05.

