5.5 Handling of Missing Values and Outliers

All data collected under this protocol will be included in the assessment of safety. For AEs missing severity and relationship, if there is no other information available, relationship will be assessed as “possible” and severity will be assessed as “severe” for summary purposes, unless there is specific justification presented to impute other values. Missing or incomplete start dates will be imputed to the date of device implantation. Outliers that may have undue influence on the analysis and results will be discussed, but the results will not be based on any exclusion.

For the analysis of the efficacy endpoints, missing data will be imputed with a Last Observation Carried Forward approach. For any missing Visit 4 baseline data; the Visit 2 measure will be used as baseline. Multiple imputation, with missing at random assumptions using SAS PROC MI will also be performed as a sensitivity analysis. Data from the control group will be used to impute the missing in the VNS group. The specific imputation model will be defined prior to database lock. For the responder analysis, subjects with missing results will be imputed as non-responders for the initial evaluation, and a tipping point analysis will be used to assess sensitivity to missing data.

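### The 80% power in SAP section 3.4 applies to 100 subjects with observed Visit 5 scores, not to the specified primary analysis of all randomised subjects with LOCF

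*SAP*

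**What the plan says.** **Size and power.** SAP section 3.4 sets the recruitment target: "The study plan is to enroll and implant up to 120 subjects in order to have approximately 100 subjects complete the study". It then gives the power: "A sample size of 100 subjects total (50 per group) will have 80% power with 0.05 alpha". The stated aim of that size is "to detect a difference of 2.3 with SD=4.0 on the FMA UE scale between the two treatment groups". The assumed arm means are "VNS having an average improvement of 7.5 from baseline, with control having an average change of 5.2 from baseline". Section 5.4 fixes the test "with significance at alpha 0.05 two sided".

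**Who is analysed.** Section 3.1: "Subjects will be randomized 1:1 on the day of implant surgery". A subject implanted under the 120 ceiling is therefore also randomised. Section 4.1: "The ITT population will include any subject who is randomized, and will be the basis of the efficacy and safety analyses".

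**Missing scores.** Section 5.5: "For the analysis of the efficacy endpoints, missing data will be imputed with a Last Observation Carried Forward approach". If Visit 4 is missing, Visit 2 becomes the baseline.

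**Endpoint and visits.** The primary endpoint is the FMA-UE change from Visit 4 to Visit 5 (section 5.3). Sections 3.3 and 4.4 show no efficacy assessment between those two visits.

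**The concern.** The step from 120 implanted to about 100 completing treats non-completers as if they drop out of the analysis and are made good by extra recruitment. Under sections 4.1 and 5.5 they do not drop out. A subject without Visit 5 has the Visit 4 score carried forward and enters the primary comparison with a change of exactly zero. If Visit 4 is missing too, Visit 2 is both the baseline and the carried value, so the change is again zero.

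The assumed mean changes are 7.5 and 5.2, so a block of zeros in each arm does two things. It shrinks the difference between arms in proportion to the share missing, and it widens the spread within each arm. The calculation in section 3.4 allows for neither.

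This is a pivotal study intended as the main support for US market approval (section 1), and the three secondary tests are all gated on the primary (section 5.4). A reader of section 3.4 would take the risk of missing a true 2.3-point effect to be 20%. For the analysis actually specified, that risk depends on how many subjects lack Visit 5, and the section does not say so.

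**Working it through.** **Inputs.** Means 7.5 and 5.2, difference 2.3, SD 4.0, 50 per group, up to 120 implanted and about 100 completing (section 3.4). Two-sided 0.05 (section 5.4). 1:1 allocation (section 3.1). LOCF (section 5.5).

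**Step 1: reproduce the stated figure.** The noncentrality is 2.3 / (4.0 × √(2/50)) = 2.3 / 0.80 = 2.875. Power is 82.0% by the normal approximation and 81.2% by noncentral t. The stated 80% reproduces.

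**Step 2: 120 analysed, nobody missing.** The noncentrality is 2.3 / (4.0 × √(2/60)) = 2.3 / 0.730 = 3.15. Power is 87.8% by t. Analysing 120 rather than 100 raises power by itself.

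**Step 3: 120 analysed, some at zero change.** Let f be the share with Visit 5 observed, the same in both arms.
- Difference = f × 2.3
- Variance in an arm with mean m = f × 16 + f(1 − f) × m²

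With 20 of 120 missing, f = 100/120 = 0.833:
- Difference = 0.833 × 2.3 = 1.92
- VNS variance = 13.33 + 0.1389 × 56.25 = 21.15
- Control variance = 13.33 + 0.1389 × 27.04 = 17.09
- Pooled SD = √((21.15 + 17.09)/2) = 4.37
- Noncentrality = 1.92 / (4.37 × √(2/60)) = 2.40, power 66.3% by t

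This formula lets the number missing vary at random in each arm. If exactly 10 are missing per arm, simulated two-sample t-tests give 69.4%.

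**Step 4: the range of Visit 5 loss, 120 randomised.**

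| Lacking Visit 5 | Difference | SD | Power, random loss (t) | Power, equal split (simulation) |
|---|---|---|---|---|
| 0 | 2.30 | 4.00 | 88% | 88% |
| 8 (6.7%) | 2.15 | 4.19 | 80% | 81% |
| 10 (8.3%) | 2.11 | 4.22 | 77% | 80% |
| 20 (16.7%) | 1.92 | 4.37 | 66% | 69% |

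Power crosses 80% at about 8 missing under random loss and about 10 under an exactly equal split.

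**Step 5: covariates.** The primary model is an ANCOVA (section 5.12), but the SAP gives no covariate correlation. With 20 missing, an assumed correlation of 0.3 gives 70.4% and one of 0.5 gives 78.5%, by scaling the SD by √(1 − r²). These are illustrations, not SAP figures.

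**The case against.** The strongest reply is that the SAP never plans for 20 losses before Visit 5. Section 3.4 does not define completing the study. Stage I runs to Visit 7, 90 days after therapy, and follow-up continues beyond that. When the SAP means the Visit 5 milestone it names it, as in the futility rule of section 3.5. Anyone lost after Visit 5 has an observed primary endpoint. The figure of 120 is also a ceiling. **This stands.** Section 3.4 leans somewhat the other way, since it uses the 100 as the number for the primary comparison and counts exposure on 100 subjects followed for 6 weeks, but that does not settle the matter. A reader might infer that the trial's planned power is 66-70%, or that its risk of missing the effect is 30-34%. The documents do not support either as the SAP's own case.

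A second reply is that the power sentence is true as written, because it is conditional on 50 per group with the full effect. **This stands too.** A reader might call the 80% an arithmetic error. It is not. The figure belongs to a different analysis.

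A third reply is that the larger analysis set is not the cause. **Correct:** 120 subjects with complete data give 88%. The whole loss comes from the zero change that LOCF assigns.

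A fourth reply is that covariate adjustment would recover some power. It may, but the SAP claims no such gain. At the assumed correlations of 0.3 and 0.5, the case with 20 missing stays below 80%.

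**Conclusion.** The point holds as a mismatch between the power statement and the specified primary analysis. The SAP-consistent range with 120 randomised runs from about 66% to 88% and straddles the stated 80%. Where the trial falls depends on Visit 5 loss, which the SAP does not state. The 80% is safe only while no more than about 8-10 of 120 (7-8%) lack Visit 5, which is half or less of the 120-to-100 allowance.

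The range rests on these assumptions: the full 120 are randomised; the same share is lost in each arm; every subject lacking Visit 5 has zero change under LOCF; the means and SD of section 3.4 hold for those observed; and no covariate gain is counted. The point concerns the stated power only. It takes no position on whether LOCF is the right rule.

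**What to change.** In section 3.4, make two changes:
- Label the 80% as applying to 100 subjects (50 per group) with observed Visit 5 data.
- Add the power of the ITT/LOCF analysis with 120 randomised over a range of Visit 5 loss, including the cases above 80%: about 88% with none missing, 80-81% with 8, 77-80% with 10, and 66-69% with 20. State that no covariate gain is counted.

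The cost is SAP wording only. Enrolment, model, analysis set and imputation rule stay as they are. The downside is a stated power that may look less favourable.

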4.4 Schedule

The table below indicates the primary, secondary, and other analysis timepoints and measures. The change between each visit and the pre-therapy baseline (V4) is the measure of interest, and the difference between the two treatment groups will be analyzed. Within-group changes will also be analyzed.

	Visit 5 (One day after 6-weeks of therapy)	Visit 7 (90 days after 6-weeks of therapy)	Long-Term (6,9,12m after 6-weeks of VNS) Or (LT4, LT5, LT6)	Crossover (Control one day after 6-weeks of VNS [LT1] compared to V7 (prior to start of VNS))
	UEFM Change (primary)	UEFM Response (2 nd)	UEFM Change (o)	UEFM Change (o)
	UEFM Response (o)	UEFM Change (2 nd)	UEFM Response (o)	UEFM Response (o)
	WMFT (o)	WMFT (2 nd)	WMFT (o)	WMFT (o)
	QOL (o)	QOL (o)	QOL (o)	QOL (o)
	BDI (o)	BDI (o)	BDI (o)	BDI (o)
	MAL (o)	MAL (o)	MAL (o)	MAL (o)

o = other (not a primary or secondary analysis)

UEFM – Upper Extremity Fugl-Meyer; WMFT – Wolf Motor Function Test

MAL – Motor Activity Log; QOL includes SIS, SS-QOL, 5Q-5D

BDI – Beck Depression Inventory (assessed as both an efficacy and a safety measure)

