5.3 Efficacy Endpoints

The primary endpoint will be the change of the FMA UE score from Visit 4 (pre-therapy, baseline) to Visit 5 (Day 1 post therapy).

There are three hierarchical secondary endpoints

1. The proportion of responders, defined as a 6-point change or greater in the FMA UE score from baseline (Visit 4) to Day 90 post treatment (Visit 7)

2. The change in WMFT from baseline (Visit 4) to Day 90 post treatment (Visit 7)
3. The change in FMA UE score from baseline (Visit 4) to Day 90 post treatment (Visit 7)

Quality of Life Endpoints

Quality of life assessments and a motor activity log will be used to provide data to support overall treatment response:

- Stroke Impact Scale (SIS): The SIS has been developed to assess eight different domains of health-related quality of life, such as emotion, communication, memory, and thinking, and social role function. Each item is rated on a 5-point Likert scale in terms of the difficulty the person has experienced in completing each item. Scores for each domain range from 0-100.
- Stroke Specific QOL (SS-QOL): The SS-QOL is a self-report questionnaire consisting of 49 items in the 12 domains of energy, family roles, language, mobility, mood, personality, self-care, social roles, thinking, upper extremity (UE) function, vision, and work/productivity.
- 5Q-5D QOL (general QOL) – EQ-5D™ is a standardized instrument for use as a general measure of health outcome. It provides a simple descriptive profile and a single index value for health status.
- Motor Activity Log (MAL) - The MAL consists of 14 activities (patient reported outcomes) of daily living (ADLs) such as using a towel, brushing teeth, and picking up a glass. For a specified time period post-stroke, the individual is asked about the extent of the activity performed and how well it was performed by the more impaired arm. The response scale ranges from 0 (never used) to 5 (same as pre-stroke).

These QOL measures are considered “tertiary” or “other” endpoints that provide further evidence of the benefits of treatment (not considered primary or secondary endpoints).

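### SAP 3.4: the 75% and 33% responder rates behind the stated power do not fit the means (7.5, 5.2) and SD (4.0) planned in the same paragraph; under normality those give about 65% vs 42% and about 62% power

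*SAP*

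**What the plan says.** Section 3.4 of the SAP makes two sets of assumptions about the same variable, the change in FMA-UE from baseline.

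- **Means.** With 50 per group, the trial is said to have 80% power "to detect a difference of 2.3 with SD=4.0 on the FMA UE scale between the two treatment groups". The text continues: "This is based on the assumption of VNS having an average improvement of 7.5 from baseline, with control having an average change of 5.2".
- **Responders.** The paragraph then says: "A sample size of 50 per group will have over 95% power at 0.05 alpha to show a difference in responders". A responder improves by at least 6 points, and the rates are given as "assuming 75% response in the VNS group and 33% in the control group".

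The section does not link the two sets and names no visit for either.

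Elsewhere the SAP has two FMA-UE responder analyses in Stage I. The table in 4.4 marks the one at Visit 5 as other ("UEFM Response (o") and the one at Visit 7 as secondary ("UEFM Response (2 nd"). Section 5.3 ranks the second of these first among the secondary endpoints, "defined as a 6-point change or greater in the FMA UE score from baseline (Visit 4) to Day 90 post treatment (Visit 7"), while the primary endpoint is the mean change at Visit 5. Section 5.4 allows significance to be declared for "each subsequent endpoint only if all higher ranked endpoints were significant at 0.05".

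**The concern.** Once a distribution is assumed, a mean and an SD determine what share of an arm reaches 6 points. The responder rates are therefore not a free second choice. If 7.5, 5.2 and 4.0 are the planning values, the responder rates should be compatible with them, or the text should say why they differ.

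At stake is how 3.4 presents the risk to the secondary endpoints. The Day 90 responder test comes first in the hierarchy. If it fails, neither the WMFT change nor the FMA-UE change at Day 90 can be declared significant. A reader of 3.4 would take that first step as close to certain, when the effect behind it is nearly twice the one that sizes the trial.

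**Working it through.** **Inputs.** From 3.4: 50 per group, alpha 0.05, cut-off 6 points, means 7.5 and 5.2, SD 4.0, rates 75% and 33%. From 5.4: two-sided testing.

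**Formula.** The test is the unadjusted two-proportion z-test with pooled variance under the null. With p̄ the average of p1 and p2, power = Φ[(p1 − p2 − 1.96·s0)/s1], where s0 = √(2p̄(1 − p̄)/n) and s1 = √(p1(1 − p1)/n + p2(1 − p2)/n).

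**1. The plan's own figures reproduce.**
- Responders, 0.75 vs 0.33: s0 = 0.0997 and s1 = 0.0904. (0.42 − 1.96 × 0.0997)/0.0904 = 2.48, so power is 99.4% (Fisher's exact test 98.8%).
- Means: 2.3/(4.0 × √(2/50)) = 2.875, so power is Φ(2.875 − 1.96) = 82.0% (t-test 81.2%), consistent with the stated 80%.

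**2. Responder rates implied by the means and SD, if changes are normal.**
- VNS: 1 − Φ((6 − 7.5)/4) = 64.6%.
- Control: 1 − Φ((6 − 5.2)/4) = 42.1%.
- The gap is 22.5 points, against the assumed 42.
- Power: s0 = 0.0998 and s1 = 0.0972. (0.2254 − 1.96 × 0.0998)/0.0972 = 0.307, so power is 62.1% (Fisher 56.6%).
- With a 5.5 cut-off, to allow for an integer score, the rates are 69.1% and 47.0% and power is 61.4%.

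**3. Means or SDs implied by 75% and 33%, if changes are normal.**
- At SD 4.0 the means are 6 + 4 × 0.674 = 8.70 and 6 − 4 × 0.440 = 4.24, a difference of about 4.5.
- At the planned means the SDs are 1.5/0.674 = 2.22 (VNS) and 0.8/0.440 = 1.82 (control), about half of 4.0.

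**4. Dependence on shape, with means 7.5 and 5.2 and SD 4.0 kept.**

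| Shape | VNS | Control | Power |
|---|---|---|---|
| Normal, both arms | 64.6% | 42.1% | 62% |
| Gamma, both arms | 58.8% | 32.8% | 75% |
| t with 5 df, both arms | 67.6% | 40.3% | 79% |
| Lognormal, both arms | 57.8% | 29.1% | 84% |
| Normal VNS, gamma control | 64.6% | 32.8% | 90% |
| t with 3 df, both arms | 71.9% | 37.6% | 94% |
| Gamma (shape 2), VNS skewed left, control skewed right | 71.9% | 33.5% | 98% |
| t with 2.5 df, both arms | 76.3% | 34.5% | 99% |

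Among the shapes tried, only strongly heavy tails or opposite skew in the two arms give about 94% or more.

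**5. Dependence on effect and SD, normal changes.**
- With control at 5.2 and SD 4.0, differences of 3.0, 3.5 and 4.0 give 84%, 93% and 97%; about 3.7 is needed for 95%.
- At the planned means, SDs of 3.5, 3.0 and 2.5 give 74%, 86% and 95%. At SD 2.5, however, the primary comparison would have 99.5% power, so that is not the setting planned.
- Moving both means together does not help; power peaks at 62%.

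**6. The planned test.** Section 5.12 uses logistic regression with the randomization strata. Simulated with normal changes and assumed stratum effects, it gives 62% to 69%, so the z-test is an adequate approximation.

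**7. Optional sensitivity.** Section 5.5 counts missing responders as non-responders. With 60 per arm and 10 missing in each (an assumption, taken from 120 enrolled and 100 completing), the normal rates become 64.6% × 50/60 = 53.8% and 42.1% × 50/60 = 35.1%, and power is about 54%.

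**The case against.** The strongest reply is that the sentence is conditional and true: given 75% and 33%, the power does exceed 95%. A reader might infer that 3.4 contains a miscalculated power. It does not, and both of its power figures reproduce.

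The second reply concerns the visit. The means belong most naturally to the primary endpoint at Visit 5, and the ranked responder endpoint is at Visit 7. In between, section 3.3 has home stimulation active in the VNS arm only, so a larger difference by Day 90 is possible. If the rates refer to Visit 5 instead, they share the primary's visit and a later effect cannot explain the gap, but that responder analysis is not ranked and nothing depends on it. This stands as a limit: carrying 7.5, 5.2 and 4.0 to Day 90 is an added assumption. It does not remove the point, because 3.4 states no growth in effect and leaves the visit open.

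The third reply is that a mean and SD do not fix a proportion. That is also right. A gamma control arm alone gives 32.8%, almost exactly the assumed 33%. A reader might infer from the symmetric cases that the answer lies between 62% and 84%. That range covers only normal, gamma and lognormal changes with the same family in both arms; other shapes give 90% or more, and the SAP names no shape.

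Finally, the source of the rates may be in the protocol, which is not at hand, so the lack of a cited source is not the complaint. The complaint is that two sets of figures in one paragraph do not fit together without a further assumption.

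**Conclusion.** The point holds as an inconsistency between planning assumptions, not as an arithmetic error. If changes are normal and the planned means and SD apply at the responder visit, implied power is about 62%, against 99.4% at the stated rates. The 62% is conditional on both assumptions. A reader might take it as the true power of the Day 90 test, but the documents do not support that, because they fix neither the shape of the changes nor the Day 90 effect. They do support a narrower conclusion: power above 95% needs a larger effect, a smaller SD or an unusual distribution, and 3.4 states none of these.

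The consequence is confined to how the power of the first-ranked secondary endpoint, and so of the two below it, is presented. The stated power of the primary comparison is sound. The change should be made, but it is not critical to the trial.

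**What to change.** Change the wording of SAP section 3.4 only:

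1. Name the visit to which the 75% and 33% refer (Day 90, if the ranked endpoint is meant).
2. Label these rates as a separate scenario, more optimistic than the one that sizes the trial.
3. Beside it, give the responder power implied by the sizing assumptions: about 62% at 50 per group, stating that this takes changes as normal and the same means and SD at that visit. Alternatively, state the larger Day 90 effect, the smaller SD or the distribution that supports more than 95%.
4. Do not print 62% to 84% as if it bounded the answer. The 54% under non-responder imputation may be added as a sensitivity figure, with its missing-data assumption stated.

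The cost is a few sentences and a less favourable figure beside the present one. Enrolment, alpha, the primary analysis and the order of the hierarchy stay as they are.
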